4.3.2.3.3 Unsolicited Adverse Events

In addition to recording solicited reactions, subjects / parents / LARs will be instructed to record any other medical events that may occur during the 30-day period after vaccination. Space will be provided in the diary card for this purpose.

Information on SAEs will be collected and assessed throughout the study, from the time of vaccination until Day 30 after vaccination. Any SAE occurring at any time during the study will be reported by the Investigator in the CRB according to the completion instructions provided by the Sponsor; this includes checking the "Serious" box on the AE CRF and completing the appropriate Safety Complementary Information CRFs. All information concerning the SAE is to be reported either as part of the initial reporting or during follow-up reporting if relevant information became available later (eg, outcome, medical history, results of investigations, copy of hospitalization reports). In case a subject experiences febrile convulsion (neurological event associating fever and seizure), the assessment will be performed according to the "Guideline for definition and collection of cases of febrile convulsion", and this event will be considered an SAE. See the protocol for further details on SAE reporting.

For each unsolicited AE (whether serious or non-serious), the following information is to be recorded:

- Start and stop dates^a
- Intensity of the event:

.

The stop date of all related AEs will be actively solicited. For other events, the Investigator will provide the stop date when it becomes available. AEs for which no stop date was obtained during the course of the study will be considered as ongoing at the end of the study.

For measurable unsolicited AEs that are part of the list of solicited reactions, the size of the AE as well as the temperature for fever will be collected and analyzed based on the corresponding scale used for solicited reactions (see Table 4.1, Table 4.2, and Table 4.3).

All other unsolicited AEs will be classified according to the following intensity scale:

- Grade 1: A type of AEs that is usually transient and may require only minimal treatment or therapeutic intervention. The event does not generally interfere with usual activities of daily living.
- Grade 2: A type of AEs that is usually alleviated with additional therapeutic intervention. The event interferes with usual activities of daily living, causing discomfort but poses no significant or permanent risk of harm to the research subject.
- Grade 3: A type of AEs that interrupts usual activities of daily living, or significantly affects clinical status, or may require intensive therapeutic intervention.
- Whether the AE was related to the investigational product (for unsolicited systemic AEs)

 The Investigator will assess the causal relationship between the AE and the investigational product as either "Not related" or "Related", as described Section 4.3.2.3.5.
- Action taken for each AE (e.g., medication)

The action(s) taken by the subject / parent or LAR to treat and/or manage any unsolicited AEs will be classified in the CRB using the following list (all applicable items should be checked):

- None
- Medication
- Health care provider contact
- Hospitalized
- Whether the AE was serious

For each SAE, the Investigator will complete all seriousness criteria that apply (outcome, elapsed time, and relationship to study procedures)

• Whether the AE caused study discontinuation

4.3.2.3.4 Adverse Events of Special Interest

An AESI is defined as event for which ongoing monitoring and rapid communication by the Investigator to the Sponsor must be done. The following AEs will be captured as AESIs throughout the study:

- Generalized seizures (febrile and non-febrile)
- Kawasaki disease
- Guillain-Barré syndrome
- Idiopathic thrombocytopenic purpura (ITP)

These events have been listed as AESIs based on the feedback received from the European Union regulators.

No safety concerns relating to these AESIs have been identified with the use of MenACYW conjugate vaccine in the completed clinical trials. Because of their medical importance and to ensure expedited communication to the Sponsor, these AESIs, are to be considered and collected as SAEs and reported to the Sponsor according to the procedure described in the protocol. Further instructions on the data collection for these events and the relevant definitions will be provided in the Operating Guidelines.

4.3.2.3.5 Assessment of Causality

The Investigator will assess the *causal relationship* between each unsolicited systemic AE and the product administered as *not related* or *related*, based on the following definitions:

- Not related The AE is clearly / most probably caused by other etiologies such as an underlying condition, therapeutic intervention, or concomitant therapy; or the delay between vaccination and the onset of the AE is incompatible with a causal relationship; or the AE started before the first vaccination (screening phase, if applicable)
- Related There is a "reasonable possibility" that the AE was caused by the product administered, meaning that there is evidence or arguments to suggest a causal relationship

Note: By convention, all AEs reported at the injection site (whether solicited or unsolicited) and all solicited systemic AEs are considered to be related to the administered product and therefore are referred to as reactions and do not require the Investigator's opinion on relatedness.

AEs likely to be related to the product, whether serious or not, that persist at the end of the study will be followed up by the Investigator until their complete disappearance or the stabilization of the subject's condition. The Investigator will inform the Sponsor of the date of final disappearance of the event or the date of "chronicity" establishment.

4.4 Derived Endpoints: Calculation Methods

4.4.1 Safety

4.4.1.1 Solicited Reactions

4.4.1.1.1 Daily Intensity

All daily records for solicited injection site and systemic reactions will be derived into daily intensity scales according to the following classification: None, Grade 1, Grade 2, Grade 3, or Missing (Unknown).

For the derivation of daily intensities, the following sequential steps will be applied:

1) Solicited reactions (except Fever/Pyrexia) with CRF presence recorded as "No" and with all daily records missing (Unknown), then all daily intensities will be derived as None.

2) For non-measurable (NM) solicited reactions, daily intensities will correspond to daily records reported in the clinical database. For measurable solicited reactions the daily measurements reported in the clinical database will be converted based upon the intensity scales defined in the protocol; this assumes a reaction that is too large to measure (NM) is Grade 3. Note the intensity could be considered "None" (not a reaction) in the analysis despite being considered a reaction by the investigator.

Note: The maximum intensity on the ongoing period is derived from the record of the maximum intensity/measurement after the end of the solicited period following the rule described above.

4.4.1.1.2 Maximum Intensity

Maximum overall intensity is derived from the daily intensities as described in Section 4.4.1.1.1 and is calculated as the maximum of the daily intensities over the period considered.

4.4.1.1.3 Presence

Presence is derived from the maximum overall intensity on the period considered:

- None: No presence
- Grade 1, Grade 2, or Grade 3: Presence
- Missing or Unknown: Missing presence

Subjects with at least one non-missing presence for a specific endpoint will be included in the safety analysis tables. Conversely, those without a non-missing presence will not be included in the analysis of the endpoint.

The time period is displayed as D0-D3, D4-D7, D8 and later.

Note: solicited reactions with Missing presence will not be included in the safety analysis tables but will be listed separately in separate listings.

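### For the six non-fever solicited reactions, a recorded reaction with no daily grades drops out of its rate, while a recorded non-reaction with no daily grades is kept

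*SAP*

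**What the plan says.** SAP 4.4.1.1.1 derives a daily intensity for each solicited reaction in two steps.

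- Step 1 covers reactions other than fever whose CRF presence is No "and with all daily records missing (Unknown), then all daily intensities will be derived as None".
- Step 2 covers everything else. For reactions graded by the subject or parent, "daily intensities will correspond to daily records reported in the clinical database". For measured reactions the size is converted to a grade, and "this assumes a reaction that is too large to measure (NM) is Grade 3".

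Under SAP 4.4.1.1.2 the maximum intensity "is calculated as the maximum of the daily intensities over the period considered". SAP 4.4.1.1.3 derives presence from that maximum: a grade means present, None means absent, and Missing means presence is Missing. For subjects in the last category it says: "Conversely, those without a non-missing presence will not be included in the analysis of the endpoint". Their reactions go to listings: "Note: solicited reactions with Missing presence will not be included in the safety analysis tables but will be listed separately in separate listings".

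SAP 5.3.1.3 sends missing solicited intensities back to 4.4.1.1.1. SAP 5.3.1 states a general policy of not replacing missing safety data, and SAP 5.7 lists no change on this point.

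**The concern.** A Yes and a No with equally empty daily grids are treated differently. The No is kept as information about occurrence. The Yes is discarded because its grade is missing, although the safety endpoints in SAP 4.3.2.2 list occurrence and intensity as separate items.

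The SAP is more cautious with unsolicited events. There an event needs only a verbatim term and an intensity other than None (4.4.1.2.1). Events with missing onset stay in the tables (4.4.1.2.4), and a missing causal relationship is taken as related (5.3.1.2). In the discontinuation tables (4.4.1.3.6) an unsolicited event counts at Grade 1 or above or with grade missing, but a solicited one only at Grade 1 or above.

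At stake are the reactogenicity rates. Describing safety is an objective in every cohort, and Protocol 5.1.2 says the study is meant to support licensing in both countries. Subjects known to have reacted could be left out of the tables.

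**Working it through.** **Tracing each kind of record through SAP 4.4.1.1.1 to 4.4.1.1.3**

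| Record for one reaction | Daily intensity | Maximum | Presence | Effect on the rate |
|---|---|---|---|---|
| Non-fever, No, no daily records | None (step 1) | None | Absent | Kept in denominator as non-reactor |
| Non-fever, Yes, no daily records | Missing (no rule) | Missing | Missing | Out of numerator and denominator; listed |
| Non-fever, Yes, at least one graded day | The grade | The highest grade | Present | Counted as reactor |
| Measurable, too large to measure | Grade 3 | Grade 3 | Present | Counted as reactor |
| Fever, Yes or No, no temperatures | Missing (outside step 1) | Missing | Missing | Both dropped alike |

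The second row is inferred from the absence of a rule, but nothing in the SAP points to another result.

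**Direction**

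- Pain, headache, malaise and myalgia: the lowest grade is Grade 1 (SAP Tables 4.1 to 4.3), so any true Yes is a reaction.
- Redness and swelling at 2 to 9 years: any size above 0 mm is Grade 1 (SAP Table 4.1), so the same holds.
- Redness and swelling at 10 years and over: Grade 1 starts at 25 mm (SAP Table 4.2), so a smaller Yes would be None in the analysis. Let X of N subjects truly reach Grade 1, let k Yes records be dropped, and let q be the share of those k that were at least 25 mm. The reported rate is (X − qk)/(N − k), which is below X/N only if q > X/N. That is likely but not assured.

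**Size, per reaction**

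The documents state no solicited-reaction rate and no number of ungraded Yes records, so there is no planned figure to reproduce. Let r be the true rate and m the share of reactors recorded Yes with no daily grades. Both are assumed, all other records are taken as complete, and each Yes as a true reaction. Then

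reported rate = r(1 − m)/(1 − rm).

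For r = 40% and m = 5%: 0.40 × 0.95/(1 − 0.02) = 0.38/0.98 = 38.78%, a shift of −1.22 points. Shifts in percentage points:

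| r | m = 1% | m = 5% | m = 10% |
|---|---|---|---|
| 5% | −0.05 | −0.24 | −0.48 |
| 20% | −0.16 | −0.81 | −1.63 |
| 40% | −0.24 | −1.22 | −2.50 |
| 60% | −0.24 | −1.24 | −2.55 |

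At m = 0 the shift is zero. In counts: Groups 5 and 7 together plan 233 + 233 = 466 subjects. With an assumed 186 reactors, 10 of them ungraded, the SAP rule gives 176/456 = 38.6%. Counting them gives 186/466 = 39.9%.

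**Fever**

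Yes and No are dropped alike. With equal missingness m the rate is r(1 − m)/[r(1 − m) + (1 − r)(1 − m)] = r, so 10% stays 10%.

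**Composite row**

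The formula does not apply to a row for any reaction. A subject with one ungraded Yes and No elsewhere has some non-missing presence and could be counted as a non-reactor. The rate would then be r(1 − m): 0.40 × 0.95 = 38.0% at m = 5%.

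**Difference between vaccines**

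- r = 40% and m = 5% in both groups: 38.78% against 38.78%, so the difference stays zero.
- r = 40% and 20%, m = 5% in both: 38.78 − 19.19 = 19.59 points instead of 20.
- r = 40% in both, m = 0 against 10%: 40.0% against 37.5%, a spurious 2.5 points.

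**The case against.** The case against has four parts.

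1. **The records may not exist.** The CRF is not among the documents, and the SAP mentions only the value No. Whether Yes can be saved with an empty grid is unknown. Protocol 11.1 has the site interview subjects and clarify incomplete entries; 11.2 provides consistency checks and queries; 13.2 provides verbal clarification of missing diary data; 13.4.1 requires queries to be completed before database lock. A single graded day is also enough to count the subject, reading the maximum as taken over recorded days. This stands: m may be close to zero.
2. **A No with an empty grid is complete, because there is nothing to grade.** True, and step 1 is reasonable. It does not justify discarding a recorded Yes.
3. **For measured reactions the SAP puts the measurement ahead of the investigator's flag** (4.4.1.1.7 does so for ongoing status). This stands for redness and swelling from age 10, and it is why the main fix should not reach them.
4. **Little depends on it.** Safety is observational, no hypothesis is tested on it, and the dropped records are listed. At r = 40% and m = 2% the rate is 0.392/0.992 = 39.5%, about 0.5 points low. The 95% half-width by normal approximation is 1.96 × √(0.24/466) = 4.4 points at n = 466, and 9.6 at n = 100. This limits the weight of the point, but a known omission from a safety table is not excused by sampling error, and listings do not correct the rate.

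A reader might also infer that all solicited rates are biased downward in every group. The documents do not support that. Fever is outside step 1, the direction is open for redness and swelling from age 10, and there is no effect without such records.

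**Conclusion.** The asymmetry is in the SAP text and is not corrected elsewhere in it. It concerns six reactions: pain, redness, swelling, headache, malaise and myalgia. If ungraded Yes records remain at analysis, the rate is understated for pain, headache, malaise and myalgia at all ages and for redness and swelling at 2 to 9 years. It is probably, but not certainly, understated for redness and swelling at 10 years and over. Fever, the only solicited reaction with an alert threshold in the Early Safety Data Review, is not affected by the asymmetry.

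The size is about 0.05 to 2.6 points per reaction. That range rests wholly on the assumed r and m. It would be tempting to conclude that the comparison between vaccines is biased; it is materially distorted only if ungraded Yes records are more frequent in one group, and nothing in the documents says they are. The primary immunogenicity test is untouched. The point is worth acting on because the correction is cheap and the present rule can drop known reactors.

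**What to change.** In SAP 4.4.1.1.1 and 4.4.1.1.3:

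- For pain, headache, malaise and myalgia at all ages, and for redness and swelling at 2 to 9 years, count CRF presence Yes with no daily intensity as present. Set intensity, onset day and number of days to Missing. Include the subject in the numerator and denominator of that reaction and of any composite row, and add a missing-grade row to the intensity table.
- For redness and swelling at 10 years and over, keep the current rule and add a sensitivity row that counts these records as present.
- Report the number of such records by group and reaction. If it is zero, the question is closed. Keep the existing listing.

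The cost is a short SAP addition, the extra table rows and a count. No new data are needed. Where such records exist, the stated reaction rates become slightly less favourable.

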4.4.1.1.4 Time of Onset

Time of onset is derived from the daily intensities as described in Section 4.4.1.1.1. It corresponds to the first day with intensity of Grade 1, Grade 2, or Grade 3 during the solicited period (D0 to D7) after each vaccination.

Note: If a reaction is not continuous (i.e., reaction occurs over two separate periods of time intervened by at least one daily intensity Missing or None) then the time of onset is the first day of the first occurrence during the solicited period (D0 to D7) after each vaccination.

Time of onset is presented as D0-D3, D4-D7.

4.4.1.1.5 Number of Days of Occurrence During the Solicited Period

Number of days of occurrence over the solicited period (D0 to D7) considered is derived from the daily intensities as described in Section 4.4.1.1.1. It corresponds to the number of days with daily intensities of Grade 1, Grade 2, or Grade 3. Number of days of occurrence on the solicited period with a specified intensity (e.g., Grade 3) may also be derived.

4.4.1.1.6 Overall Number of Days of Occurrence

If a reaction is ongoing at the end of the solicited period, then the overall number of days of occurrence after each vaccination is derived from the daily intensities and the stop date of the reaction after the end of the solicited period. The overall number of days of occurrence is:

(End date – last vaccination date) + (number of days of occurrence within the solicited period) – length of the solicited period + 1

If the end date of the solicited reaction is missing or is incomplete (contains missing data), the overall number of days of occurrence will be considered as Missing.

4.4.1.1.7 Ongoing

Ongoing is derived from the last daily intensity of the solicited period as described in Section 4.4.1.1.1 and the maximum intensity on the ongoing period. The investigator's ongoing flag is not used because the measurement would determine the ongoing status of the reaction.

- Ongoing: if the last daily intensity of the solicited period is at least Grade 1 and the maximum intensity on the ongoing period is at least Grade 1
- Not ongoing: if the last daily intensity of the solicited period is None or the maximum intensity on the ongoing period is None.
- Missing: all other conditions (in this case, it is not included in the denominator of the ongoing analysis in the safety tables).

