An unsolicited AE is an observed AE that does not fulfill the conditions prelisted in the CRB in terms of diagnosis and/or onset window post-vaccination. For example, if headache between D0 and D07 is a solicited reaction (i.e., pre-listed in the protocol and CRB), then a headache starting on D07 is a solicited reaction, whereas headache starting on D08 post-vaccination is an unsolicited AE. Unsolicited AEs includes both serious (SAEs) and non-serious unsolicited AEs.

Injection Site Reaction:

An injection site reaction is an AR at and around the injection site. Injection site reactions are commonly inflammatory reactions. They are considered to be related to the product administered.

Systemic AE:

Systemic AEs are all AEs that are not injection or administration site reactions. They therefore include systemic manifestations such as headache, fever, as well as localized or topical manifestations that are not associated with the vaccination or administration site (e.g., erythema that is localized but that is not occurring at the injection site).

Adverse Event of Special Interest (AESI):

An AESI is an event for which ongoing monitoring and rapid communication by the Investigator to the Sponsor must be done.

Such an event might warrant further investigation in order to characterize and understand it. Depending on the nature of the event, rapid communication by the study Sponsor to other parties (e.g., regulators) might also be warranted.

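### SAP 4.4.1.1.7 keeps half-recorded reactions whose known half is negative and drops those whose known half is positive, so the share ongoing after Day 7 is likely to be understated

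*SAP*

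**What the plan says.** SAP 4.4.1.1.7 sorts each solicited reaction into three classes.

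- Ongoing needs both records to be positive: "last daily intensity of the solicited period is at least Grade 1 and the maximum intensity on the ongoing period is at least Grade 1".
- One negative record is sufficient for the opposite class: "Not ongoing: if the last daily intensity of the solicited period is None or the maximum intensity on the ongoing period is None".
- The remainder leaves the table: "Missing: all other conditions (in this case, it is not included in the denominator of the ongoing analysis in the safety tables".

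The investigator's own entry is set aside, with the reason that the "ongoing flag is not used because the measurement would determine the ongoing status of the reaction".

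SAP 4.4.1.1.6 governs length and starts from the same status: "If a reaction is ongoing at the end of the solicited period, then the overall number of days of occurrence after each vaccination is derived". The inputs are the daily grades and the stop date. Its only rule for missing data concerns the end date. It does not say what happens to length when the ongoing status itself is Missing. SAP 5.3.1 makes no general replacement of missing safety data, and SAP 5.3.1.4 imputes no end dates for ongoing solicited reactions. The SAP describes no count, bounds or sensitivity analysis for undetermined ongoing status.

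**The concern.** Reactions that outlast the diary week are the tail of the reactogenicity profile that the safety objectives set out to describe. The classification lets one known negative settle the status but gives one known positive no weight, so blanks do not fall evenly on numerator and denominator. A reaction with a positive half seems more likely to be truly ongoing than the average retained reaction, and those are the ones removed.

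Two features sharpen the point.

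- The reason for ignoring the investigator's flag presupposes a measurement. It has no force where the post-D7 record is blank. It fits poorly for pain, headache, malaise and myalgia, four of the seven solicited reactions, which are graded by the subject or parent and not measured.
- Elsewhere the SAP resolves safety gaps towards inclusion. Missing causality counts as related (5.3.1.2), events with missing onset stay in the tables (4.4.1.2.4), and unsolicited events without a stop date are treated as ongoing (4.3.2.3.3).

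Blanks around D7 are plausible in Cohort II, where the diary card is not reviewed and collected until V02, at D30 to D44.

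**Working it through.** The documents give no ongoing share, missing-record rate or expected length, so there is no figure of the plan's own to reproduce. Every rate below is an assumption.

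**Step 1: enumerate the rule.** Let L be the last daily intensity of D0–D7, read here as the D7 record, and M the maximum intensity after D7.

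| L | M | Class | In denominator |
|---|---|---|---|
| Grade ≥1 | Grade ≥1 | Ongoing | yes |
| None | any, or blank | Not ongoing | yes |
| Grade ≥1 or blank | None | Not ongoing | yes |
| Grade ≥1 | blank | Missing | no |
| blank | Grade ≥1 | Missing | no |
| blank | blank | Missing | no |

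Of the four half-recorded states, the two with a known negative are kept and the two with a known positive are dropped.

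**Step 2: effect when M is missing at random and L is complete.** Let p be the share of reactions with L ≥ Grade 1, q the share of those with M ≥ Grade 1, and m the share of M records that are blank.

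- True share = pq.
- Retained = (1 − p) + p(1 − m) = 1 − pm.
- Reported share = pq(1 − m)/(1 − pm).
- Reported/true = (1 − m)/(1 − pm), which does not depend on q.

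| p | m = 10% | m = 20% |
|---|---|---|
| 5% | 0.90/0.995 = 0.905 | 0.80/0.99 = 0.808 |
| 20% | 0.90/0.98 = 0.918 | 0.80/0.96 = 0.833 |
| 40% | 0.90/0.96 = 0.938 | 0.80/0.92 = 0.870 |

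The range is about 81–94% of the true share. In counts: of 100 reactions, 20 have L ≥ Grade 1 and 16 of these are truly ongoing (16.0%). Losing M in 20% of the 20 leaves 12.8 ongoing among 96, which is 13.3%. At m = 10% the figure is 14.7%.

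Full enumeration with L also blank in 5–10% and M blank in 10–30% gives 66–91% of the true share. This takes p = 5–40% and q = 50–80%, and assumes no reaction absent on D7 returns later.

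**Step 3: direction when blanks are informative.** Keep p = 20%, m = 20% and 80% ongoing among recorded L-positives. Let d be the true ongoing rate among the dropped reactions. The true share is 0.2 × (0.8 × 0.8 + 0.2d) = 0.128 + 0.04d, and the reported share stays at 13.3%.

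| d | True share | Reported minus true |
|---|---|---|
| 0 | 12.8% | +0.5 points |
| 20% | 13.6% | −0.3 points |
| 80% | 16.0% | −2.7 points |
| 100% | 16.8% | −3.5 points |

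Break-even is d = 13.3%, the rate among the retained reactions. The report is too low when d is above that and slightly too high when it is below.

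**Step 4: length.** With an 8-day solicited period the formula in 4.4.1.1.6 is correct: present daily on D0–D7 and stopped on D9 gives 9 + 8 − 8 + 1 = 10 days. It adds no bias of its own. The gap is in when it applies. Take Grade 1 or more on D1–D6, D7 blank, Grade 1 after D7, and a stop date of D12. The formula would give 12 + 6 − 8 + 1 = 11 days. The status is Missing, however, and the SAP does not say whether the length is 11 days, the 6 in-window days, or missing.

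**The case against.** The strongest defence is logical. Ongoing is a conjunction, so one None disproves it and one positive half does not prove it. On that view no reaction is mislabelled, and leaving undetermined cases out follows the general policy of not replacing missing safety data (Protocol 12.3.1, SAP 5.3.1). This stands as far as labels go. It does not rescue the percentage, because a denominator that keeps half-known negatives and loses half-known positives is biased even when blanks occur at random.

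A reader might infer that a blank D7 with a later grade is certainly ongoing, because "whereas headache starting on D08 post-vaccination is an unsolicited AE". The documents do not go that far. For time of onset, SAP 4.4.1.1.4 lets a missing day split a reaction into two periods, so a gap at D7 could hide a stop and return. Treating such a case as Ongoing is a reasonable convention, not a known fact. A recorded None on D7 is different and is rightly Not ongoing.

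The exclusion of the investigator's flag also has a sound basis for measured reactions. SAP 4.4.1.1.1 notes that a finding may be None in the analysis although the investigator regards it as a reaction. From age 10, redness or swelling below 25 mm falls under Grade 1 (SAP Table 4.2). An unrestricted flag fallback would mix two definitions. This limits the remedy but does not touch the four graded reactions.

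There are safeguards against blanks. Unclear diary entries are clarified at interview (Protocol 11.1) and missing diary data are obtained verbally (Protocol 13.2). Adults have a D8 review (Protocol 5.1.4.1), and Cohort II has a reminder contact at D8–D10 (Protocol 5.1.4.2). These should lower the missing rate, by an amount the documents do not give.

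Finally, the share ongoing after D7 is not itself a listed endpoint, the rule is the same in every group, and no hypothesis depends on it. That limits the importance of the point and is accepted.

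**Conclusion.** The asymmetry is in the text, and under plausible conditions it understates the share of reactions ongoing after D7. With post-D7 records missing at random in 10–20%, the reported share is about 81–94% of the true one. In the worked case 16.0% becomes 13.3%. These sizes rest wholly on assumed rates.

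Two stronger readings should be resisted. One is that the bias is always downward: if post-D7 fields are blank because the reaction had ended, the share is slightly overstated (by 0.5 points in the worked case when none of the dropped reactions was ongoing). The other is that the rule shortens the reported length of reactions. That is possible, but SAP 4.4.1.1.6 is silent on length when ongoing status is Missing, so it is not established.

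Only descriptive safety tables are affected; the primary non-inferiority analysis is not. The change is worth making because it is cheap and uses items the SAP already refers to.

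**What to change.** Amend SAP 4.4.1.1.7 as follows.

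1. Where D7 is blank (not None) and the post-D7 maximum is Grade 1 or more, class the reaction as Ongoing.
2. Where D7 is Grade 1 or more and the post-D7 maximum is blank, resolve the status in either direction from the stop date or the investigator's flag for pain, headache, malaise and myalgia. For erythema, swelling and fever do this only as a sensitivity analysis, because the flag may reflect findings below the Grade 1 threshold.
3. Leave D7 = None as Not ongoing.
4. Report the number of unresolved statuses per group, with a lower bound counting all of them as not ongoing and an upper bound counting all as ongoing. In the worked case the bounds are 12.8/100 = 12.8% and (12.8 + 4)/100 = 16.8%, which contain the true 16.0%.

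In SAP 4.4.1.1.6, state that length is computed from the stop date, where one exists, for reactions resolved in this way.

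The cost is SAP wording and a small derivation change, with no new data collection. How often the stop date and flag are filled in cannot be judged without the case report form. The reported share of prolonged reactions may rise slightly.
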